6.2 SUMMARIES OF CONDUCT OF STUDY

Enrollment, study treatment administration, and discontinuation from the study will be summarized overall and by treatment arm. The incidence of study treatment discontinuation for reasons other than disease progression will be tabulated.

6.3 SUMMARIES OF TREATMENT GROUP COMPARABILITY

Demographic variables, stratification factors, and other baseline characteristics will be summarized by treatment arm.

6.4 EFFICACY ANALYSES

The primary and secondary efficacy analyses will include the ITT population; that is, all randomized patients will be included in the analyses, with patients grouped according to the treatment assigned at randomization.

6.4.1 Primary Efficacy Endpoint

The co-primary efficacy endpoints are (1) tumor ORR, assessed by modified RECIST criteria by breast MRI (centrally assessed) and (2) the rate of pCR in breast and axilla (total pCR) after completion of study drug.

The tumor ORR will be calculated by treatment arm in all enrolled population and in *PIK3CA* MT population. Within each population, the ORR for the two treatment arms will be compared at a two-sided alpha of 16% using a Cochran Mantel-Haenszel test, stratified by tumor size and nodal status. The pCR rate will also be calculated and compared at a two-sided alpha of 4% based on the same analytical approach as ORR. The two alpha values account for a family-wise type I error rate of 20% *for each analysis*

population. Patients with early study termination and hence missing efficacy outcome will be considered as non-responders.

6.4.2 Secondary Efficacy Endpoints

The secondary efficacy endpoints for this study are as follows:

- Tumor ORR after completion of study treatment, assessed by modified RECIST criteria by breast MRI (centrally assessed) in *PIK3CA* WT patients.
- Rate of pCR in breast and axilla (total pCR) after completion of study drug in *PIK3CA* WT patients.

These endpoint measures will be summarized by treatment arm and will be analyzed analogue to the primary efficacy endpoint.

The following secondary efficacy endpoints will be performed in all enrolled patients and separated by *PIK3CA* mutation status (centrally assessed):

- ORR using modified RECIST criteria by the following methods: clinical breast examination, mammography, and breast ultrasound
- Ki67 values at baseline, Week 3, and surgery (centrally assessed)
- Change in Ki67 from baseline to Week 3; baseline to surgery, and Week 3 to surgery (centrally assessed)
- PEPI score (centrally derived)
- Change in enhancing tumor volume from baseline to surgery as measured by breast MRI
- Evaluation of different definitions of pCR including the following: a) ypT0, ypN0, and b) ypT0/is, ypNX (breast pCR)

These endpoint measures will be summarized by treatment arm and will be compared between the two treatment arms within each population based on appropriate statistical analyses: ORR will be compared using a Cochrane Mantel-Haenszel test, stratified by tumor size and nodal status; PEPI, Ki67, and tumor volume change will be compared by regression analyses, adjusted for tumor size and nodal status. All secondary endpoints will be tested at a two-sided type I error of 5%.

More details of the analyses will be provided in the Statistical Analysis Plan (SAP).

6.5 SAFETY ANALYSES

Safety analyses will include all patients who received at least one dose of study treatment, with patients allocated to the treatment arm associated with the regimen actually received.

Safety will be assessed through summaries of adverse events, changes in laboratory test results, changes in vital signs, and letrozole and GDC-0032 exposure.

Verbatim descriptions of adverse events will be mapped to thesaurus terms. Adverse event data will be listed by study site, treatment arm, patient number, and study day, severity, relationship to study drug, outcome, and action taken with the study treatments. Events occurring on or after treatment on Day 1 of Week 1 will be summarized by thesaurus term, appropriate thesaurus levels, and NCI CTCAE, v4.0 grade. Serious adverse events, including deaths, will be listed separately and will be summarized.

Relevant laboratory and vital sign (heart rate, blood pressure, and temperature) data will be displayed by time, with NCI CTCAE, v4.0 Grade 3 and 4 values identified, where appropriate. Additionally, all laboratory data will be summarized in tables by NCI CTCAE, v4.0 grade.

6.6 PHARMACODYNAMIC ANALYSES

Ki67 biomarker analyses will include patients with at least one predose and one postdose biomarker assessment, with patients grouped according to the treatment actually received.

6.7 PHARMACOKINETIC ANALYSES

Individual C_{max} and trough plasma concentrations (C_{min}) of GDC-0032 and letrozole from all patients enrolled will be reported. Mean of trough plasma concentrations of GDC-0032 and letrozole will be tabulated. The population pharmacokinetics of letrozole and GDC-0032 in this study will be compared with historical single-agent pharmacokinetics to assess the potential DDI between GDC-0032 and letrozole in this population.

Additional PK analyses on metabolites of GDC-0032, letrozole, and/or other concomitant medications may be conducted as appropriate.

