1.7.1.1 Preliminary Pharmacokinetics

Pharmacokinetic (PK) data are available from 34 patients treated with GDC-0032 at 3, 5, 8, 12, and 16 mg in the ongoing Phase I/II clinical trial (Study PMT4979g). The cohort mean apparent clearance and the terminal half-life ($t_{1/2}$) following a single, oral dose of GDC-0032 had a range of 4.77–9.17 L/hour and 36.7–43.8 hours, respectively. Following daily oral dosing for 8 days, there was a 2- to 4-fold accumulation of GDC-0032. The pharmacokinetics of GDC-0032 appears to be dose linear and time-independent. Preliminary PK data from Cohort E suggest there is no drug-drug interaction (DDI) between letrozole plus GDC-0032. Mean plasma exposure of letrozole when given in combination with GDC-0032 (maximum concentration observed [C_{max}]=0.407 μM and area under the concentration–time curve from 0 to 24 hours [AUC_{0-24}] = 8.01 $\mu\text{M}\cdot\text{hr}$) was comparable with the historical single-agent exposure (C_{max} =0.495 μM and AUC_{0-24} = 10.1 $\mu\text{M}\cdot\text{hr}$) ([Awada et al. 2008](#)). Similarly, plasma concentrations of GDC-0032, when given in combination with letrozole, were within the range predicted by the population PK model. Therefore, letrozole plus GDC-0032 can be co-administered without the risk of a DDI.

GDC-0032 was metabolized primarily by CYP3A4 in human liver microsomes (HLMs) and appeared to be a weak time-dependent inhibitor of CYP3A4. Although in vitro induction studies in human hepatocytes suggested that GDC-0032 has low to moderate potential to induce CYP3A4, preliminary data from the Phase I/II study (PMT4979g) indicate that 9 mg of GDC-0032 daily for 2 weeks in patients had no apparent effect on the pharmacokinetics of midazolam (a sensitive CYP3A4 substrate). Therefore, GDC-0032 may be administered concomitantly with CYP3A4 substrates without the risk of a PK DDI.

Preliminary data from a healthy volunteer study showed that the 3-mg GDC-0032 tablet produces an estimated geometric mean ratio (90% CI) of 196% (177.1–217.0) for C_{max}

and 152.2% (141.9–163.2) for AUC time 0 to infinity (AUC_{0-inf}) when compared with the 3-mg Phase I capsule. For this reason, a new 2-mg tablet has been formulated to deliver GDC-0032 exposure similar to the 3-mg capsule formulation.

[figure not shown]

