3. STUDY DESIGN

3.1 DESCRIPTION OF STUDY

This is a two-arm, randomized, double-blind, multicenter, pre-operative study to evaluate the effect of combining letrozole and GDC-0032 versus letrozole and placebo in postmenopausal women with ER+/HER2- untreated, Stage I–III operable breast cancer whose primary tumors are ≥ 2 cm. Patients with cT4 or cN3 tumors are not eligible.

[figure not shown]
Standard of care assessments/procedures (e.g., bilateral mammogram) performed within 28 days of Day 1 dosing do not need to be repeated for screening purposes.

All patients will undergo pretreatment tumor tissue acquisition (snap-frozen [optimal cutting temperature; OCT] and formalin-fixed paraffin-embedded cores [FFPE]). Two pretreatment FFPE core biopsies and one freshly frozen core biopsy must be obtained for all patients prior to beginning study drug treatment. Tumor tissue from prior diagnostic FFPE core biopsies may be used for enrollment eligibility purposes. For the purpose of enrollment, ER, progesterone receptor (PR), and HER2 will be locally determined prior to beginning of study treatment. Remaining tissue will be retained for future translational studies. Presurgical sentinel lymph node biopsy (SLNB) is not allowed.

Patients will be randomized into one of the two treatment arms with a 1:1 randomization ratio. Letrozole at 2.5 mg will be dosed once daily plus either GDC-0032 at 4 mg (two 2-mg tablets) or placebo on a 5–days-on/2–days-off schedule for a total of 16 weeks (see [Figure 5](#)). A maximum of 16 weeks of GDC-0032 can be administered. Letrozole can be continued up to surgery per the investigator's discretion.

Figure 5 Study Schema

Letrozole 2.5 mg QD + GDC-0032 4 mg or placebo QD on a 5-days-on/2-days-off schedule

	Pretreatment	Day 15 (Week 3)	Week 9	Week 16	Surgery (Week 17-18)
Tumor tissue	●	●			●
MRI	●		●	●	
Breast U/S	●		●	●	
Mammogram	●			●	

BC=breast cancer; ER+=estrogen receptor positive; HER2=Human Epidermal Growth Factor Receptor 2; MRI=magnetic resonance imaging; QD=once daily; U/S=ultrasound.

After confirmation of all the eligibility criteria, patients will be randomized to one of the treatment arms. A second biopsy will be performed on Day 15 (Week 3) for biomarker analyses. Biopsies should be performed at least 2 hours after GDC-0032 dose administration.

Randomization will be stratified according to 2 factors:

1. Tumor size (T1-T2 vs. T3)
2. Nodal status (cytologically positive vs. radiologically or cytologically negative)

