
The study will enroll approximately 330 patients at approximately 110 global sites.

At Weeks 1, 5, 9, 13, and 16 the primary breast tumor and axillary lymph nodes will be assessed by clinical breast examination (palpation and caliper measurement).

Suspicion of progression based on clinical exam at any time should be further evaluated (see [Figure 6](#)).

In addition to the safety assessments conducted at the scheduled follow-up visits, patients will be contacted by telephone for a general assessment of adverse events at Weeks 7 and 11.

[figure not shown]
At Week 9, a breast ultrasound will be performed to ensure that there is no progressive disease and for the purpose of surgery planning. Suspicion of progressive disease on breast ultrasound should be confirmed by investigator-assessed breast MRI. Patients with primary disease not evaluable by ultrasound at baseline should be assessed by MRI at Week 9. Suspected progression in nodes should also be confirmed by fine needle aspiration (FNA) if these nodes had not been previously shown to be cytologically positive for cancer. Patients with progressive disease (as defined by modified RECIST, [Appendix 3](#)) can either proceed directly to surgery or be taken off of the study, according to the investigator's decision. If the patient goes off-study, every reasonable effort should be made to obtain a new biopsy sample prior to beginning another systemic treatment.

From Week 13, the patient will visit with the surgeon. The purpose of this visit is two-fold: tentative planning of the type of breast surgery to be performed (breast conservative vs. mastectomy) and scheduling the date for definitive surgery.

During Week 16, breast MRI will be done for the purpose of primary endpoint analysis. Clinical breast examination, breast ultrasound, and mammography will also be conducted prior to surgery for the purpose of the secondary endpoint analysis.

Blood samples for exploratory endpoint analysis will be collected on Day 1 prior to dosing, at Week 9, prior to surgery (*Week 16 visit,*) and at the 4-weeks postsurgical follow-up visit.

Figure 6 Schematic Representing Confirmation of Progression

FNA=fine needle aspiration; MRI =magnetic resonance imaging; PD=progressive disease.

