3.4.4 Exploratory Outcome Measures

The exploratory outcome measures for this study are as follows:

- ORR, pCR rate, and PEPI scores according to the decrease in Ki67 after 2 weeks of letrozole plus GDC-0032 and letrozole plus placebo.
- Expression of biomarkers before, during, and after therapy. These include but are not limited to the following:
 - PI3K pathway aberrations
 - Gene signatures, including intrinsic subtyping and PI3K pathway activity
 - Hormone receptor expression levels
 - Protein and phospho-protein markers and combinations
 - Mutations within cancer-associated genes
 - Copy number alterations in cancer-related genes
 - Plasma-based protein biomarkers
 - ctDNA
- Compare the rates of BCS and conversion to BCS in letrozole plus GDC-0032 versus letrozole plus placebo
- The relationship between GDC-0032 concentration and tumor response and/or drug safety response
- Letrozole concentrations with and without administration of GDC-0032
- The relationship between pharmacogenetic differences in drug metabolizing enzymes and transporters and other patient-specific covariates with PK of GDC-0032 or letrozole and/or drug response
- Changes from baseline to surgery in the apparent diffusion coefficient (ADC), a marker of tumor cellularity derived from diffusion-weighted MRI
- Concordance of the different imaging modalities (MRI [volume, enhancement, diffusion metrics], ultrasound, mammography) in measuring tumor response

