4.2.3 Blinding

Investigators and patients will be blinded to treatment assignment of GDC-0032 or placebo.

For emergency situations, the investigator will be able to break the treatment code by contacting the IxRS. The responsibility to break the treatment code in emergency situations resides solely with the investigator. For non-emergency situations, the investigator needs to obtain approval from the Medical Monitor to break the treatment code. Unblinding during the study will result in the withdrawal of a patient from the study. For regulatory reporting purposes, and if required by local health authorities, the Sponsor will break the treatment code for all serious, unexpected, suspected adverse reactions that are considered by the investigator or Sponsor to be related to study drug.

While PK samples must be collected from patients assigned to the comparator arm to maintain the blinding of treatment assignment, PK assay results for these patients are generally not needed for the safe conduct or proper interpretation of this trial. The PK assay group will be unblinded to patients' treatment assignments to identify appropriate PK samples to be analyzed and bioanalytical methodology to employ. However, the PK scientist does not have access to the PK assay results and therefore stays blinded until the PK assay results need to be interpreted and reported. Samples from patients assigned to the comparator arm will be analyzed for letrozole. However, GDC-0032 assay will be analyzed by request (i.e., to evaluate a possible error in dosing).

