Appendix 2 Schedule of Pharmacokinetic Assessments

Visit	Timepoint	PK Assessments
Day 1	3 hours post (± 60 min) letrozole and GDC-0032/placebo administration	Letrozole PK
		GDC-0032 PK
Day 15 (+ 2 days)	0–4 hours prior to letrozole and GDC-0032/placebo administration	Letrozole PK
		GDC-0032 PK
	3 hours (± 60 min) post letrozole and GDC-0032/placebo administration ECG before PK	Letrozole PK
		GDC-0032 PK
Day 57 (+/- 2 days)	3 hours post (± 60 min) letrozole and GDC-0032/placebo administration	Letrozole PK GDC-0032 PK

ECG=electrocardiogram; min=minutes; PK=pharmacokinetics.

Record exact time of dose administration and sample collection.

Appendix 3

Modified Response Evaluation Criteria in Solid Tumors: Assessment of Response of Neoadjuvant Therapy in Early Breast Cancer

Conventional response criteria may not be ideal for the assessment of response in the setting of neoadjuvant therapy in early breast cancer. Therefore, RECIST 1.1 criteria have been modified to specifically address assessment of primary breast lesions along with axillary lymph node disease, using a range of breast imaging modalities. Selected sections from the Response Evaluation Criteria in Solid Tumors (RECIST), Version 1.1¹ are presented below, with modifications and the addition of explanatory text as needed for clarity. For detailed information on the read methodology including how imaging data should be processed prior to reads, please refer to the Study Imaging Charter.

	RECIST v1.1	Modified RECIST Early Breast Cancer Neoadjuvant Therapy
Modalities	CT as primary modality, ultrasound not recommended	No CT; primary assessments by MRI; also assessments by ultrasound, mammography, and clinical exam
Lymph nodes	May be considered target lesions based on size criteria (≥ 15 mm in SAD)	Only axillary lymph nodes assessed; nodes that are considered abnormal on imaging (based on morphological factors including, but not limited to SAD) to be followed as non-target lesions
Possibility of having only non-target disease	Allowed	Not allowed; primary breast lesions must be measurable by MRI

CT=computed tomography; MRI=magnetic resonance imaging; SAD=short axis dimension.

BASELINE DOCUMENTATION OF TARGET AND NON-TARGET LESIONS

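### Section 6.7 judges the effect of GDC-0032 on letrozole against historical data, although the randomised placebo arm supplies a concurrent comparison

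*Protocol*

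**What the plan says.** Section 6.7 of the protocol names one interaction analysis: the population pharmacokinetics of both drugs "in this study will be compared with historical single-agent pharmacokinetics to assess the potential DDI between GDC-0032 and letrozole in this population". It also has individual peak and trough levels reported for all enrolled patients and mean troughs tabulated. It does not say whether letrozole results are split by arm.

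Other sections supply a concurrent control:

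- Section 3.1: "Patients will be randomized into one of the two treatment arms with a 1:1 randomization ratio", one arm being letrozole plus placebo. Planned size: "The study will enroll approximately 330 patients at approximately 110 global sites".
- Section 3.4.4, among the exploratory outcome measures: "Letrozole concentrations with and without administration of GDC-0032".
- Section 4.2.3: "Samples from patients assigned to the comparator arm will be analyzed for letrozole". The same paragraph says that comparator-arm PK results are generally not needed to interpret the trial properly.
- Appendix 2: letrozole is sampled at 3 hours post-dose on Days 1, 15 and 57, and once pre-dose on Day 15, "0–4 hours prior to letrozole and GDC-0032/placebo administration". The timing is tied to GDC-0032 or placebo, so both arms follow it.

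Section 1.7.1.1 already contains one historical comparison from the Phase I/II study. It reports that letrozole exposure in combination "was comparable with the historical single-agent exposure" and concludes that the two drugs can be given together without interaction risk.

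**The concern.** The outcome measure asks what GDC-0032 does to letrozole levels. Randomisation supplies patients on letrozole without GDC-0032, treated over the same period and measured with the same assay. Section 6.7 instead names a comparison with patients from other studies. A difference found that way may be an interaction, or it may come from the population, the sampling or the assay. A finding of no difference is open to the same doubt.

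The question is not idle on the protocol's own account. Section 4.4.1 says that letrozole is cleared mainly by CYP2A6 and CYP3A4, and that GDC-0032 can induce CYP3A4 in vitro. The same section reports no apparent effect of 9 mg daily on midazolam, and Section 3.3.13 calls an interaction unlikely. The clinical data behind that view are labelled preliminary (10 patients in Section 4.4.1, 24 in Section 3.3.13). At stake is a clear answer to an exploratory objective, and with it some help in reading the efficacy result.

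**Working it through.** The protocol gives no sample size, margin or precision for the interaction assessment, so there is no planned figure to reproduce. The check has three parts.

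**1. What the existing historical comparison can show.** Inputs from Section 1.7.1.1: letrozole with GDC-0032, Cmax 0.407 µM and AUC(0–24) 8.01 µM·hr; historical letrozole alone, 0.495 and 10.1.

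- Cmax ratio: 0.407 / 0.495 = 0.82 (18% lower).
- AUC ratio: 8.01 / 10.1 = 0.79 (21% lower).

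Suppose, as an assumption, that the historical letrozole level is anywhere from 0.80 to 1.25 times the level a concurrent control would show. The apparent ratio is the true ratio divided by that factor.

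- No interaction: 1 / 0.80 = 1.25 down to 1 / 1.25 = 0.80.
- True ratio 0.793: 0.793 / 0.80 = 0.99 down to 0.793 / 1.25 = 0.63.

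So a shift of this size between studies could produce an apparent ratio close to 0.79 with no interaction, or hide a true 0.79 almost completely.

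**2. What the randomised comparison would give.** Inputs: 330 patients at 1:1, so 330 / 2 = 165 per arm. The between-patient CV of letrozole levels is not in the protocol and is assumed to lie between 30% and 100%. On the log scale s = √ln(1 + CV²), and the 90% confidence limits are the estimated ratio multiplied and divided by exp(1.645 · s · √(2/165)).

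For CV 30%: s = √ln 1.09 = 0.294; √(2/165) = 0.110; 1.645 × 0.294 × 0.110 = 0.053; exp(0.053) = 1.055. The last two columns give power to detect a ratio of 0.793 at a two-sided 5% level (also an assumption).

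| Assumed CV | 90% CI factor, 165 per arm | Power, 330 patients | Power, 231 patients (30% of samples lost) |
|---|---|---|---|
| 30% | 1.055 | >99% | >99% |
| 50% | 1.089 | 99% | 96% |
| 70% | 1.121 | 92% | 80% |
| 100% | 1.163 | 72% | 56% |

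With 231 patients the CI factor runs from 1.066 to 1.197 over the same range of CV.

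**3. A side effect of the wording.** Section 6.7 does not say that letrozole in this study is split by arm. If both arms were pooled against history, a true ratio of 0.793 would shrink to √0.793 = 0.89 (geometric) or (1 + 0.793) / 2 = 0.90 (arithmetic). This shows the cost of leaving the split unstated; it is not a claim that pooling is planned.

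**The case against.** The strongest reply is that the between-arm comparison is already implied. The placebo arm is the only in-trial source of letrozole levels without GDC-0032, its samples are assayed for letrozole, and levels are reported for all patients. The objective is exploratory, Section 6.9 leaves further exploratory detail to the SAP, and the SAP is not at hand. Much of this stands. It makes the point a mismatch between Sections 3.4.4 and 6.7, and it keeps it minor. It does not remove it: Section 6.7 does not leave the comparator open but names the historical one, so an SAP that made the randomised comparison the main analysis would depart from the protocol.

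A reader might infer more, and the documents do not support it:

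- *That the efficacy comparison is confounded.* If GDC-0032 lowers letrozole levels, that is part of the effect of adding GDC-0032 in a randomised add-on trial. Knowing it would help interpretation; it removes no bias, because none arises from this.
- *That the GDC-0032 half of the historical comparison is equally faulty, because earlier dosing was daily and by capsule.* The trial has no arm on GDC-0032 alone, so history is the only comparator. Section 6.7 compares population pharmacokinetics, not raw troughs, which are only tabulated. Appendix 2 has exact dose and sampling times recorded, which such a model can use. The only pre-dose sample is on Day 15; there is no Day 57 trough.
- *That the ratios of 0.79 and 0.82 show an interaction.* They are preliminary Phase I/II figures against another study and cannot separate an interaction from a study difference.

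**Conclusion.** The point holds for letrozole only. Section 6.7 states a weaker method than the trial's own design supports, and it does not carry through the outcome measure in Section 3.4.4. The randomised comparison would give 90% confidence limits within a factor of about 1.06 to 1.16 of the estimated ratio, assuming 165 evaluable patients per arm and a between-patient CV of 30% to 100%. That is narrow enough to resolve a reduction of about 20% over most of the assumed range, less surely at a CV of 100% or with heavy sample loss. The CV range, the 5% level used for power and the 0.80 to 1.25 shift between studies are assumptions, not protocol figures. Severity is minor: the objective is exploratory, and no primary or secondary efficacy analysis changes.

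**What to change.** Add to Section 6.7:

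> The effect of GDC-0032 on letrozole is assessed primarily by comparing letrozole concentrations between the randomised arms (Day 15 pre-dose, and 3 h post-dose at Day 15 and Day 57) as geometric mean ratios with 90% CI; comparison with historical letrozole data is supportive.

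Keep the historical population-PK comparison for the effect of letrozole on GDC-0032. In Section 4.2.3, qualify the remark that comparator-arm PK results are generally not needed, so that it agrees with assaying those samples for letrozole.

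The cost is wording only. The named time points are all in Appendix 2, and the comparator-arm letrozole assays are already planned, so no sample, visit or assay is added.
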